5.3.4 Concomitant medication

See Section 6.5, for details in restricted or prohibited medications.

5.3.5 Blood donation

Patients should not donate blood whilst participating in studies of AZD7648 and for at least 12 weeks after receiving the last dose of study treatment.

5.4 Screen failures

Screen failures are defined as patients who signed the ICF to participate in the clinical study but are not subsequently dosed with study treatment. A minimal set of screen failure information is required to ensure transparent reporting of screen failure patients to meet the Consolidated Standards of Reporting Trials (CONSORT) publishing requirements and to respond to queries from Regulatory authorities. Minimal information includes demography, screen failure details, eligibility criteria, and any SAE.

Individuals who do not meet the criteria for participation in this study (screen failure) may be rescreened. Rescreened patients should be assigned the same patient number as for the initial screening. However, rescreening should be documented so that its effect on study results, if any, can be assessed.

These patients should have the reason for screen failure recorded in the case report form (CRF).

6 STUDY TREATMENTS

Study treatment is defined as any investigational product(s) (including marketed product comparator and placebo) or medical device(s) intended to be administered to a study

participant according to the study protocol. Study treatment in the Core Module refers to AZD7648 (Table 3).

Further details on the combination treatment administered in Combination Module 1 can be found in Section 14.1.

6.1 Treatments administered

6.1.1 Investigational products

Table 3	Study treatments
---------	------------------

Study treatment name:	AZD7648
Dosage formulation:	Provided as mg, mg, mg, mg, mg, and mg mg white film-coated oral tablets. The mg and mg tablets are round. The mg and mg tablets are caplet shaped.
	Note: In accordance with Quality IMPD, other intermediate strengths may be added at a later date.
Route of administration:	Oral tablets
Starting dose instructions:	During Part A (dose escalation), a single dose of AZD7648 will be administered in the clinic (CCI) to enable collection of blood samples for PK analyses. This is followed by a CCI In cohort 1, at CCI the starting dose and schedule of AZD7648 is mg CCI on a CCI . AZD7648 will be administered orally on an empty stomach. On clinic days, patients should not take the study treatment until instructed to do so by clinic staff.
Packaging and labelling:	 Study treatment will be provided in high-density polyethylene bottles. The bottles are induction sealed and closed with child-resistant polypropylene screw caps. Study treatment should be kept in a secure place under appropriate storage conditions. The investigational product label on the bottle specifies the appropriate storage. Each bottle will be labelled in accordance with Good Manufacturing Practice Annex 13 and per country regulatory requirement. Label text will be translated into local language. The site must complete the Patient Diary with the details of the dosing instructions at the time of dispensing.
Provider:	AstraZeneca

6.1.2 Dose escalation scheme – Core Module

The dose escalation study flow chart for the Core Module is presented in Figure 6; further details on the dose escalation for Combination Module 1 can be found in Section 14.1.2

AZD7648 will be administered as an oral dose, initially CC (refer to Figure 7). The individual patient observation period will be for the duration of the sampling as detailed in the SoA (Table 1). When there is more than one patient enrolled to a dose cohort, sentinel dosing will be applied with a single patient exposed for a minimum of 48 hours after Cycle 1, Day 1 before further patients are enrolled at that dose level. In the absence of any significant toxicities in the first patient, the patients for the remainder of the cohort may be enrolled, concurrently or sequentially, based upon the decision of the SRC.

If significant toxicities are observed during the first 48 hours of observation in the first patient of the cohort, further enrolment into the cohort will be halted until the SRC has reviewed all the safety data (and the PK data for Cohorts 1 to 4) for that patient and cumulative data from all trial patients to determine the appropriate action.

Figure 6 AZD7648 monotherapy study flow chart

RP2D=recommended Phase II dose.

Where dosing is **CCI** the tablets should be taken approximately 12 hours apart. If a dose is missed, it is acceptable to take the scheduled dose up to 2 hours after the scheduled dose time. If greater than 2 hours, the missed dose should not be taken, and the patient should continue with the next dose at the allotted time. If vomiting occurs shortly after AZD7648 is swallowed, the dose should not be replaced. Resume dosing at the following scheduled dose.

Table 4 is an example dose escalation scheme. However, all potential dose escalation levels after the starting dose may be adjusted in light of emerging safety, tolerability, and/or PK data (see Section 4.3.1). Intermittent schedules may also be explored in the Core Module from Cohort 2 onwards.

Cohort	AZD7648 dose (mg), CCI unless otherwise stated
1	
2	
3	
4	
5	
6	
7	CCI
8	CCI
Cohort n (escalate to MTD or MFD)	No more than 50% increment
Maximum dose level	CCI

Table 4Example of AZD7648 monotherapy dose escalation scheme

I=CCI ; MFD=maximum feasible dose; MTD=maximum tolerated dose; CCI

Actual doses and schedules may vary using Bayesian adaptive design modelling based on emerging safety and tolerability data, and/or pharmacokinetic (PK) data, and subject to Safety Review Committee (SRC) agreement. A maximum of dose doubling using single patient cohorts may be permitted up to and including

the **C** mg **C** cohort, if the following conditions are met:

No common terminology criteria for adverse event (CTCAE) Grade ≥ 2 drug related toxicity.

SRC provides the recommendation following the review of all available data (and informed by real-time PK analysis for Cohorts 1 to 4).

Figure 7 Starting dose and schedule for AZD7648 monotherapy

Using an accelerated titration design, single patient cohorts may be enrolled up to and including \bigcirc mg \bigcirc provided that there is no CTCAE Grade ≥ 2 drug-related toxicity and with agreement by the SRC (informed by real-time PK analysis for Cohorts 1 to 4). From \bigcirc mg \bigcirc a minimum of 3 patients (and maximum of 6 patients) will be enrolled in each subsequent cohort. At the RP2D up to 12 patients may be treated to explore chronic toxicity. For SRC meetings prior to dose escalation where 3 patients have been enrolled, at least 2 patients will need to be evaluable for DLT. However, if patients are receiving treatment

within the DLT assessment period, the dose escalation review meeting should be deferred so that the SRC accounts for all patient data.

Dose escalation and de-escalation will follow the Bayesian adaptive design below.

If no DLT at any dose has been observed, then dose escalation may occur without modelling. Dose doubling may be permitted in single patient cohorts up to and including mg CCI if recommended by the SRC (informed by 'real-time' analysis of PK samples for Cohorts 1 to 4). However, if CTCAE Grade ≥ 2 drug-related toxicity is observed or at the recommendation of the SRC, cohorts may be expanded to recruit a minimum of 3 (and maximum of 6) patients in all subsequent cohorts.

From CCI (or once cohorts are recruiting a minimum of 3 patients), after the first DLT has been observed (at any dose), a Bayesian logistic regression model will be used to inform subsequent dose selections. After each cohort, cumulative data on the evaluable patients will be used to estimate the predicted probability of a DLT at each potential next dose.

- The recommendation for the next dose will be based on the following principles:
 - The recommendation for the next dose will be chosen to target a DLT of 25% for monotherapy and 30% for combination but ignoring any dose for which the model suggests the probability of a DLT exceeds 35%. This will allow efficient identification of the MTD whilst restricting the risk of overdosing.
- Dose escalation and de-escalation will be completed when any of the following occur:
 - The target toxicity of 25% (for monotherapy) and 30% (for combination) is reached and the required precision of the estimated MTD is achieved (ie, the ratio of the upper/lower 95% credible interval limits for the estimated MTD < 5.0).
 - The maximum number of evaluable patients for the dose escalation cohort has been reached.
 - There is no anticipated improvement in efficacy with increasing dose.
 - The MFD is achieved.
 - Decision made by the SRC to stop dose escalation.
- Prior established dose toxicity relationship at doses at which 10% and 50% (or similar) of patients experience DLTs will be used to inform the Bayesian model.
- Emerging data from the Core Module or any combination module of this study may also be used to inform the Bayesian model in another module of this study or other clinical studies.
- Dose increases will be permitted after review of data from a minimum of 2 out of the 3 patients enrolled into each dose cohort (data from all evaluable patients will be used to make the dose escalation decision).

There is no minimum time period required between completion of dosing in the last evaluable patient from one cohort and the start of dosing in the subsequent cohort.

To account for the dose range between the starting dose and target dose level, intra-patient dose escalations is permitted as part of the monotherapy dose escalation to maximise patient benefit and minimise exposure to non-efficacious doses. However, the following criteria must be fulfilled before a patient is permitted to proceed with an intra-patient dose escalation:

- The planned next higher dose must have been declared tolerated by the SRC (based on assessment of 2 to 6 evaluable patients).
- Agreement by the SRC that the patient is permitted to have an intra-patient dose escalation.
- Intra-patient dose escalation occurs on Day 1 following a scheduled scan assessment.

Whilst a patient is being considered for an intra-patient dose escalation, they should continue treatment at their allotted dose level. In the event of an intra-patient dose escalation, such patients will not be evaluable for DLT at the escalated dose.

After each patient has completed the DLT assessment period during the dose escalation phase of the study, the SRC will evaluate all available toxicity information (including AEs and laboratory abnormalities that are not DLTs), as well as available PK and PD information for the first cycle for all evaluable patients (data from Cycle 2 and beyond will also be evaluated if available). Additional CRF data may be included in the SRC review including vital signs, clinical chemistry/haematology, ECG results, PK and PD data, ad hoc safety reports, AEs from previous cohorts and optional expansions and any other emerging data. If appropriate, quantitative dose/exposure-response models will be used to describe the relationship for such data of interest to decide the next dose and/or schedule.

There is no limit to the number of intra-patient dose escalations that a patient can undergo.

Intermediate dose levels, dosing intervals and/or frequency, and/or schedules may be evaluated prior to declaring the RP2D, which will be guided by the evolving safety, preliminary efficacy, PK and PD data.

For decisions on dose escalation (Part A), an evaluable patient is defined as a patient that has received AZD7648 and either:

• Has completed minimum safety evaluation requirements and has received at least 75% of the total amount of planned dose of AZD7648 (and PLD for Combination Module 1) during Cycle 1

or

• Has experienced a DLT during Cycle 0 or Cycle 1.

Triggers for Additional Modules

Combination modules, eg, Combination Module 1 (combination of AZD7648 + PLD) will start after PK data from monotherapy dose escalation has confirmed an understanding of the metabolic profile of AZD7648 and the dose selected as the starting dose for the combinations is safe and tolerated. Triggers that will initiate the start of additional combination modules may include (but are not limited to):

- PK dose proportional. PK exposure vs. dose is well understood.
- Total drug exposure levels ≥ 50% of that predicted to be required for biological activity for a period defined for the specific combination. It is anticipated that the combination modules will be triggered once exposure (based on clinical PK exposure and emerging safety and tolerability data) is determined to be in a suitable therapeutic range.
- No toxicity red flags eg, DLT rate greater than that anticipated for a tolerated cohort.

Multiple combination modules may be triggered simultaneously.

6.1.2.1 Optional Expansion Cohorts

In all modules of the study, Part A cohorts may be expanded at doses at or above the MBAD in parallel to continuing the dose escalation cohorts provided that the dose has been declared as tolerated. Using this design, tolerability and PK will be characterised in the Part A population whilst providing evidence of PD and clinical activity in the populations most likely to benefit from drug and potentially across several doses.

The optional Part A expansion cohorts may be initiated for 3 reasons:

- **PD expansion cohort** of up to 12 additional patients to obtain mandatory serial biopsies for signal searching of biological PD activity.
- Efficacy expansion cohorts of up to 25 additional patients (of which a subset of up to 12 in each cohort may have mandatory biopsies if PD data is also required) to explore clinical benefit.
- **Food effect expansion cohorts** of up to 12 patients at doses between the MBAD and RP2D.

The expansion cohorts will also explore further the tolerability, safety and PK activity at these doses.

Food Effect

At least one cohort may investigate the effect of food on AZD7648 PK. If a food effect cohort is included in the monotherapy expansion cohort, then up to 12 evaluable patients may be

AstraZeneca

included in the food effect cohort if the dose and schedule has already been declared tolerated by the SRC.

If the dose and schedule has not yet been declared tolerated, then initially up to 6 evaluable patients will be enrolled to the food effect cohort, and an additional 6 evaluable patients may be added once the dose and schedule has been declared tolerated by the SRC. A cross over design will be used for the food effect cohort. Each patient will be allocated to receive a single oral dose of AZD7648 on Cycle 0, Day 1 in either the fasted or fed state, followed by a single oral dose of AZD7648 in the other state for Cycle 1, Day 1 at least 72 hours later. Other criteria may be used for decision-making based on emerging AZD7648 PK data. After Cycle 1, Day 1 patients may continue to receive AZD7648 monotherapy (at or below the RP2D and schedule), and all dosing from that point onwards must be administered in the fasted state. For the fed dosing day, patients should ideally start the recommended meal 30 minutes prior to the planned administration of the study drug. The study drug should be administered 30 minutes after the start of the meal (or up to 45 minutes after the start of their meal if the patients couldn't complete at least 75% of their meal within 30 minutes). Patients will be considered evaluable if they completed at least 75% of their meal before the administration of the study drug and the study drug is administered between 30 to 45 minutes after the start of the meal. For the fasted state, patients must fast (water only) for ≥ 10 hours prior to taking a dose to ≥ 2 hour post-dose. For the fed state patients must fast overnight (minimum of 8 hours) prior to consuming a standardised meal in the clinic. The meal should consist of about 800 to 1000 total calories with around 54% of the calorific content made up from fat. The dose should be administered with 240 mL of water. Refer to Appendix I for full details.

6.1.3 Definition of dose-limiting toxicity

DLTs will be evaluated during Cycle 0 and Cycle 1 of treatment. Toxicity will be graded according to the National Cancer Institute CTCAE v5.0.

A DLT is defined as an AE that occurs from the first dose of study treatment up to and including Cycle 1, Day 28 (the DLT assessment period) that is assessed as unrelated to the disease, intercurrent illness, or concomitant medications and that, despite optimal therapeutic interventions, meets any of the following criteria:

Haematological Toxicities:

- Grade 4 neutropenia lasting > 4 days.
- Grade 4 thrombocytopenia.
- Grade \geq 3 neutropenia (ANC < 1000 cells/mm³ [< 1 x 10⁹/L]) of any duration accompanied by fever \geq 38.5°C and/or systemic infection.
- Grade \geq 3 thrombocytopenia (< 50,000/mm³ [< 50 x 10⁹/L]) with bleeding.

Non-haematological Toxicity CTCAE Grade ≥3 Including:

- Confirmed laboratory abnormalities greater than 72 hours of duration.
- Nausea or vomiting for more than 3 consecutive days despite administration of maximal anti-emetic therapy.
- Diarrhoea for more than 3 consecutive days despite administration of maximal anti-diarrhoeal therapy.
- QTc prolongation > 500 milliseconds or QTcF prolongation from baseline by 60 milliseconds confirmed on at least 2 separate ECGs.
- Any other toxicity that is greater than that at baseline AND is clinically significant and/or unacceptable, and does not respond to optimal therapeutic intervention within 72 hours AND is judged to be a DLT by the SRC.
- Any treatment-related event, including significant dose reductions, omissions or delays, judged to be a DLT by the SRC. Examples may include CTCAE Grade 2 toxicities that are clinically significant and/or unacceptable according to the Investigator, toxicities that result in an inability to administer at least 75% of study treatment during Cycle 1 or delay the administration of study treatment in the subsequent cycle by ≥ 7 consecutive days.

DLT Will not Include the Following:

- Transient isolated laboratory abnormalities which are not considered clinically significant and resolve to baseline within 72 hours without any intervention.
- Alopecia.
- Toxicity unrelated to treatment eg, related to the underlying disease or disease-related process under investigation.
- Grade 4 vomiting and diarrhoea lasting < 72 hours in the absence of maximal medical therapy.
- Grade 3 nausea, vomiting or diarrhoea that lasts < 48 hours and resolves to Grade ≤ 1 either spontaneously or with maximal medical therapy.
- Grade 3 fatigue < 5 days.
- Grade 3 hypertension in the absence of maximal medical therapy.
- Grade 3 electrolyte abnormalities that resolve to Grade ≤ 1 within 48 hours spontaneously or with conventional medical intervention and is not clinically complicated.
- Grade 3 rash that resolves to Grade ≤ 1 within 3 weeks.
- Grade 3 or Grade 4 elevation in serum amylase and/or lipase that are not associated with clinical or radiographic evidence of pancreatitis.

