6.1.4 Safety review committee

The SRC Remit document for this study will define the exact membership and who will be present for decisions to be made.

The SRC will guide all dose escalation and cohort expansion decisions in this study. The dose or schedule for subsequent cohorts or a decision to stop recruitment will be agreed by the SRC after review of the data from each cohort. When there are other patients that are ongoing at the time a review is planned, the SRC should defer their decision until these further patients become evaluable. The data which will be reviewed at a dose decision meeting includes (but is not limited to):

- All available safety information and laboratory abnormalities (including clinically significant AEs and laboratory safety variables).
- Data on exposure eg, any dose interruptions or reductions.
- All available PK (mandatory Cycle 0 and Cycle 1 PK data in single patient cohorts up to and including ^{CCI} for Cohorts 1 to 4) and PD data.
- The dose recommended from the Bayesian model.

The SRC can decide at each meeting to:

- Determine DLTs
- Change the schedule of drug administration
- Stagger enrolment into a cohort based on toxicity in the sentinel patient
- Stop enrolment into a cohort
- Recommend a temporary halt on further dosing of patients to allow further evaluation of patients
- Stop further dosing of all patients in the study

- Escalate the dose
- Expand the cohort to a maximum of 6 evaluable patients
- De-escalate the dose
- Initiate the combination modules of AZD7648
- Stop the dose escalation
- Adjust the dosing frequency, schedule or sequence of AZD7648, with or without a concurrent change in dose
- Adjust the dosing frequency, schedule or sequence of the combination agent, with or without a concurrent change in dose
- Initiate optional expansion cohorts (PD and/or efficacy expansion and/or food effect cohorts)
- Declare the MTD, MFD, and/or RP2D for the Core Module or combination modules
- Initiate Part B cohort expansions
- Stop Part B of a study module
- Permit a patient to dose escalation (intra-patient dose escalation).

Investigators will be provided with written confirmation of the next dose level based upon the SRC decision. Regulators/ethics bodies will be formally notified, as required by local regulation, of an SRC recommendation to temporarily halt or prematurely stop the study.

6.2 **Preparation/handling/storage/accountability**

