For Combination Module 1, informative prior estimates of dose-toxicity relationship from relevant internal and external studies will be combined with prior estimates of AZD7648 dose-toxicity relationship emerging from the Core Module (monotherapy) of the study. The model incorporates terms for each monotherapy and for the combination (interaction term). A non-informative prior will be used for the interaction term.

A minimum of 3 and a maximum of 6 patients per cohort will be enrolled in Part A cohorts. For SRC meetings prior to dose escalation where 3 patients have been enrolled, at least 2 patients will need to be evaluable for DLT. However, if patients are receiving treatment within the DLT assessment period, the dose escalation review meeting should be deferred so that the SRC accounts for all patient data. Additional CRF data may be included in the SRC review including vital signs, clinical chemistry / haematology, ECG results, PK and PD data, ad hoc safety reports, AEs from previous cohorts and optional expansions and any other emerging data.

Dose escalation and de-escalation will follow the Bayesian adaptive design described in Section 6.1.2.

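### The SRC may escalate from about Day 29, roughly 7 days before a Cycle 2 delay of at least 7 days, which the protocol names as a possible DLT, can be established

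*Protocol*

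**What the plan says.** **The definition.** Protocol section 6.1.3 counts events from first dose to Cycle 1 Day 28, and section 4.1.2 agrees. The last bullet of its DLT criteria lets the SRC judge any treatment-related event a DLT. Its examples include "CTCAE Grade 2 toxicities that are clinically significant and/or unacceptable according to the Investigator", and toxicities that "or delay the administration of study treatment in the subsequent cycle by" 7 or more consecutive days.

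**When the SRC must wait.**
- Section 6.1.2, for patients on treatment: "within the DLT assessment period, the dose escalation review meeting should be deferred so that the SRC accounts for all patient data". Section 14.1.2 repeats the rule for Combination Module 1.
- Section 6.1.4, where other patients are ongoing at a planned review: "the SRC should defer their decision until these further patients become evaluable".

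**When a patient without a DLT is evaluable.** Section 6.1.2 gives the condition as "Has completed minimum safety evaluation requirements and has received at least 75% of the total amount of planned dose of AZD7648" during Cycle 1, with PLD added for Combination Module 1. It sets no Cycle 2 condition.

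**The next cohort.** Section 6.1.2 states: "There is no minimum time period required between completion of dosing in the last evaluable patient from one cohort" and the start of the next. Cycle 2 data go to the SRC only if they happen to be available.

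**The concern.** One named example of a DLT can be observed only after the DLT period has closed, and no stated rule makes the SRC wait for it. A patient can finish Cycle 1, count as evaluable, and then be held at Cycle 2 Day 1 for toxicity that arose in Cycle 1. If the SRC meets in that week, it may treat the patient as a non-DLT although the 7-day example is still open. Any resulting error runs towards the higher dose. It matters most where the cohort has the minimum number of evaluable patients and no DLT has yet been seen, because then "If no DLT at any dose has been observed, then dose escalation may occur without modelling".

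**Working it through.** **Inputs**
- Cycle length of 28 days with no interval (Protocol Table 1, footnote a).
- End of the DLT period: Cycle 1 Day 28 (section 6.1.3).
- Delay threshold: 7 consecutive days (section 6.1.3).
- Cycle 2 Day 1 visit window: ±1 day (Tables 1 and 13).
- Core Module washout after Cycle 0: 3 to 7 days (Synopsis). It may be shortened or dropped (section 8.5).
- Sentinel interval: 48 hours after Cycle 1 Day 1 (section 6.1.2).
- Minimum evaluable: 2 of 3 enrolled patients (section 6.1.2).

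**Step 1: when the example is known.** Days are counted from Cycle 1 Day 1. A 28-day cycle ends on Day 28, which reproduces the protocol's own end of the DLT period.
- Cycle 2 Day 1 = 28 + 1 = Day 29 (28 to 30 with the window).
- A dose exactly 7 days late = 29 + 7 = Day 36 (35 to 37).
- Earliest review not deferred = 28 + 1 = Day 29.
- Gap = 36 − 29 = 7 days (6 to 8 with the window).

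**Step 2: does a stated rule cover the gap?** Take a patient who has met the Cycle 1 evaluability condition and is held on Day 29.
- Sections 6.1.2 and 14.1.2: the DLT period is over, so deferral no longer applies.
- Section 6.1.4: the patient is already evaluable, so deferral no longer applies.
- Interval between cohorts: none is required.

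The SRC is therefore permitted, though not obliged, to decide before Day 36.

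**Step 3: can such a patient occur?** Section 6.6 requires ANC of at least 1500/mm³ and platelets of at least 75,000/mm³ on Day 1 of a cycle. The neutropenia criteria in section 6.1.3 start below 1000/mm³ and then need fever, infection, or Grade 4 lasting more than 4 days. For platelets the criteria are below 50,000/mm³ with bleeding, or Grade 4. An ANC between 1000 and 1500, or platelets between 50,000 and 75,000, holds Cycle 2 without meeting a listed haematological criterion. After Day 22 the next scheduled bloods are at Cycle 2 Day 1, so a Day 29 review may coincide with the first sign of the hold.

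**Step 4: effect on the cohort count.** One changed status moves 0/3 (0%) to 1/3 (33%), or 0/2 (0%) to 1/2 (50%). These are raw proportions, not model outputs.

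**Step 5: who could be dosed higher before Day 36 (Core Module).** Assume that the decision and the next sentinel's Cycle 0 dose both fall on Day 29. The washout is counted as in SAP section 3.1, where a 7-day washout puts Cycle 1 Day 1 on study day 8.

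| Washout | Sentinel Cycle 1 Day 1 | Others may enter (48 h later) | Days before Day 36 |
|---|---|---|---|
| 3 days | 29 + 3 = 32 | 32 + 2 = 34 | 36 − 34 = 2 |
| 5 days | 29 + 5 = 34 | 34 + 2 = 36 | 0 |
| 7 days | 29 + 7 = 36 | 36 + 2 = 38 | none |
| dropped | about 29 | about 29 + 2 = 31 | about 36 − 31 = 5 |

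With a 3-day washout, others entering on Day 34 receive only the single Cycle 0 dose before Day 36, because their own Cycle 1 starts no earlier than 34 + 3 = Day 37. The Combination Module 1 washout is redacted, so its timing is not calculated.

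**The case against.** The best reply is that DLT status does not depend on Day 36. The delay is an example under an open rule. The SRC can judge the underlying toxicity a DLT on Day 29, including a clinically significant Grade 2 event. It reviews all safety and laboratory data and any dose interruptions, and it can pause, stagger, de-escalate or re-score later. This stands, and it is the main reason the point is small.

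The SRC remit and the Cohort Management Plan were not supplied, and the required minimum safety evaluations are not defined in the supplied text. Any of these may already cover the case. This also stands, so the finding is about the stated rules only.

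The Day 29 assumption in the exposure estimate is tight, since investigators must first receive written confirmation of the dose. That stands too. Escalating without the model adds little, because a patient scored as a non-DLT would enter the model as a non-DLT as well.

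One argument is weak: that the delay bullet sits under the heading for non-haematological toxicity of Grade 3 or higher, so a hold for low counts falls outside it. The bullet covers any treatment-related event and cites Grade 2 toxicities, so it is not confined to that heading.

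**Conclusion.** The mismatch is in the text. The stated rules let the SRC escalate from about Day 29, roughly 7 days before a Cycle 2 delay of at least 7 days can be established (about Day 36, range 35 to 37). It is a cheap improvement of low severity. Early exposure at the higher dose is mainly one sentinel patient. Later cumulative review limits it, and the SRC minutes used by the SAP can carry a corrected status.

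A reader might infer more, and the documents do not support it:
- That a 7-day delay is automatically a DLT. It is an example left to SRC judgement.
- That the SRC must score a held patient as a non-DLT, or must escalate. It may do neither.
- That DLTs are undercounted or the MTD is set too high. The documents give no frequency of such holds and no basis for a model-based shift. Section 6.1.3.1 also requires at least 6 evaluable patients for the MTD and brings data beyond Cycle 1 into the RP2D.

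The conclusion assumes that the documents not supplied add no waiting rule. The exposure estimate also assumes the Day 29 timing in Step 5.

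**What to change.** **Protocol wording.** In sections 6.1.2, 6.1.4 and 14.1.2, add one sentence: where a patient's Cycle 2 start is held for treatment-related toxicity, the escalation decision is deferred until dosing resumes or the delay reaches 7 days, and the SRC minutes any changed DLT status. The cost is about 7 days from a Day 29 review, and none when no patient is held. Because the SAP records that development has been halted, this wording now serves mainly as a lesson for later protocols.

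**Usable now.** Before database lock, compare each patient's actual Cycle 2 Day 1 date with the DLT status in the SRC minutes, and refer any toxicity delay of at least 7 days to the SRC for judgement. The dosing and DLT data are already to be listed (SAP section 4.2.1), and SAP section 2.2 already schedules a pre-lock meeting on analysis sets. SAP Table 2, footnote b takes DLT status from the latest minutes before data cut-off, so a judgement made after that date would need a documented exception. The cost is one comparison, plus SRC review of any patient flagged.
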